3.3 Discontinuation from Study Treatment

Patients will be discontinued from study treatment for any of the following reasons:

- Irreversible or intolerable toxicity or abnormal laboratory values thought to be related to drug toxicity
- Conditions requiring therapeutic intervention not permitted by the protocol
- Intercurrent illness (this will be at the Investigator's discretion)
- Inability of the patient to comply with study requirements
- Patient requests to discontinue treatment, but agrees to finish study procedures
- Patient withdraws consent from the study and is discontinued from the study
- Non-compliance/lost to follow-up
- Pregnancy and breastfeeding
- Further participation would be injurious to the patient's health or well-being, in the Investigator's medical judgment

CONFIDENTIAL

STUDY DRUG: QUIZARTINIB
 PROTOCOL DATE: 10 AUGUST 2020

DEVELOPMENT INNOVATIONS STUDY NUMBER: AML 48
 VERSION 4.0

- The study is terminated by the Sponsor, Sarah Cannon Development Innovations (“Development Innovations”) or the Institutional Review Board (IRB)

After discontinuation from protocol treatment, patients must be followed for adverse events (AEs) for 30 days after their last dose of study drug. All new AEs occurring during this period must be reported and followed at the site until resolution for AEs attributed to the study medication(s).

4. PATIENT REGISTRATION

The patient must willingly consent to participate after being informed of the procedures to be followed, the experimental nature of the treatment, potential benefits, treatment alternatives, side-effects, risks, and discomforts. Institutional Review Board (IRB) approvals of this protocol and consent form are required. Eligible patients who wish to participate in the study will be enrolled into the study.

Registration must occur prior to the initiation of protocol therapy. Patients eligible to participate in the study may be enrolled by each site following the patient registration instructions provided by the Sarah Cannon Development Innovations (Development Innovations) study contact. Patient registration follow-up and/or confirmation will be provided via email within approximately 24 hours or by the next business day.

5. STUDY DESIGN

This is a multi-center, non-randomized, open-label, two-part prospective Phase II clinical trial in patients with relapsed or refractory FLT3-ITD mutation-positive AML. The study is designed to assess the safety and tolerability as well as the efficacy of administering CPX-351 (cytarabine:daunorubicin liposome complex) with quizartinib, a second-generation FLT3 inhibitor. The plan for administration is divided into three phases: induction, consolidation, and maintenance. Approximately 34 patients are planned to be screened and enrolled. Patient participation is expected to be 4 years.

A total of 10 patients will be enrolled in the safety lead-in. The safety lead-in portion of the study is designated as Part 1. If >3 patients experience delayed neutrophil count recovery >56 days from the first day on the study regimen, or delayed thrombocytopenia recovery >56 days from the first day on the study regimen, or if >3 patients develop a non-hematologic toxicity, defined as a Grade 4 non-hematologic adverse event determined to be probably related to the combined treatment, or a Grade 4 neutropenia, then the study will be terminated.

Assuming safety parameters are met, the first 10 patients will be followed for response in the Part 2 of the study. An additional 24 patients will be enrolled in Part 2 of the study (induction, consolidation and maintenance). All patients will be assessed for response.

Patients who fail to respond to therapy will be followed until a new therapy is instituted. . Patients who experience an AE that results in the discontinuation of study treatment will be

[figure not shown]
CONFIDENTIAL

STUDY DRUG: QUIZARTINIB
PROTOCOL DATE: 10 AUGUST 2020

DEVELOPMENT INNOVATIONS STUDY NUMBER: AML 48
VERSION 4.0

followed until resolution/stabilization for AEs attributed to the medication. Outcomes for all patients will be assessed for 24 months from the date of last treatment.

Figure 1 Study Schema

*All treatment phases follow a 28-day cycle. Induction and re-induction consist of: CPX-351 (liposomal daunorubicin 44 mg/m² IV and cytarabine 100 mg/m² IV) + quizartinib 30 mg PO QD. The maintenance phase: begin quizartinib 30 mg PO QD on Days 1-14. If there are no toxicities and QTcF is maintained ≤ 450 msec, increase dose to 60 mg QD on Day 15.

[†]For one cycle

[‡]For up to two cycles

CONFIDENTIAL

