Study Drug, Dose, and Mode of Administration:	
Induction phase: CPX-351 (daunorubicin 44 mg/m² IV and cytarabine 100 mg/m² IV) will be given on Days 1, 3, and 5 followed by 30 mg quizartinib by mouth (PO) once daily on Days 8-21. Patients with an incomplete response, but a >50% reduction in the blast count/cellularity ratio compared to the most recent bone marrow (BM) biopsy prior to treatment, should receive one additional cycle of induction therapy (re-induction) with CPX-351 (daunorubicin 44 mg/m² IV and cytarabine 100 mg/m² IV) on Days 1 and 3 only. Re-induction will begin after a 72-hour washout period from the last dose of quizartinib. During re-induction, treatment with quizartinib will resume on Day 6 and continue through Day 21. Any patient with neutropenia or thrombocytopenia lasting ≥ 56 days from the initiation of CPX-351 will not receive consolidation and will instead proceed to the maintenance phase.
 
Consolidation phase: At the Investigator's discretion, patients who achieve CR and do not proceed to an alloHCT or other CT intervention will proceed to the consolidation phase beginning 7 days (± 7) after neutrophil recovery (ANC >1000/μL). Administer up to 2 consolidation cycles of CPX-351 (daunorubicin 29 mg/m² IV and cytarabine 65 mg/m² IV) on Days 1 and 3. Begin quizartinib 30 mg PO once daily on Days 6-21.
 
Maintenance phase: Maintenance dosing of quizartinib will begin at 30 mg/day on Days 1-14, and if there are no non-hematologic Grade ≥ 3 toxicities, the quizartinib dose will increase to 60 mg/day on Day 15. The maintenance phase is a 28-day cycle beginning 7 days (± 7) after neutrophil recovery (ANC >1000/μL) from the consolidation phase or induction phase. Patients will receive quizartinib once daily for a total of 24 cycles or until disease relapse

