
Statistical Methodology:
	
A response rate (CR + CR with incomplete hematologic recovery [CRi]) of $\geq 50\%$ is targeted, with 40% or less considered unacceptable. This is assumed to be an acceptable estimate based on CR + CRi/CRp of 48.2% reported with quizartinib monotherapy in a relapsed or refractory patient with FLT3-ITD AML (Cortes et al, 2019). Of note, prior FLT3-targeting inhibitor exposure is permitted on this study. However, patients receiving a prior FLT3-targeting inhibitor were excluded in the QUANTUM-R study. Expected CR+CRi in relapsed or refractory patients receiving standard intensive or non-intensive salvage chemotherapy harboring an FLT3 mutation is 27%. The estimated response in those with relapsed/refractory FLT3-ITD AML receiving CPX-351 alone cannot be estimated. However, in a poor-risk EPI patient population, CR+CRi was reported as 39.3% (Cortes et al 2015). However, FLT3-ITD mutation presence was not utilized in the generation of EPI prognostication, and those with FLT3-ITD mutation could in fact have a reduced response within all EPI risk groups. Thus, the expected response must be based upon the QUANTUM-R study of those receiving standard salvage options harboring a FLT3-ITD mutation.
 
In the safety lead-in, 10 patients will be enrolled to receive CPX-351 with quizartinib. If >3 patients experience delayed neutrophil count recovery >56 days from the first day on the study regimen, or delayed thrombocytopenia recovery >56 days from the first day on the study regimen, or if >3 patients develop a non-hematologic toxicity, defined as a Grade 4 non-hematologic adverse event determined to be probably related to the combined treatment, or a Grade 4 neutropenia, then the study will be terminated.
 
Assuming safety parameters are met, the first 10 patients will be followed for response in Part 2 of the study.
 
The null hypothesis that the overall response rate (ORR, defined as CR + CRi) is $\leq 27\%$ will be tested against a one-sided exact alternative ORR of 50% at a target significance level of 0.05. A sample size of 30 evaluable patients achieves 80% power if the true overall response rate is $\geq 50\%$. The null hypothesis will be rejected if 13 or more responses are observed in 30 evaluable patients. In order to allow for a non-evaluable rate of 10%, a total of 34 patients will be enrolled in the study.

--	--

CONFIDENTIAL

STUDY DRUG: QUIZARTINIB
 PROTOCOL DATE: 10 AUGUST 2020

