5.2.2 Induction Phase

Treatment consists of CPX-351 (liposomal daunorubicin $44 \text{ mg}/\text{m}^2$ IV and cytarabine $100 \text{ mg}/\text{m}^2$ IV) on Days 1, 3, and 5 followed by quizartinib (30 mg by mouth [PO] once daily) on Days 8-21. If there is a PR at the recovery BM biopsy, patients may be re-treated with one additional induction therapy (re-induction) with CPX-351 (daunorubicin $44 \text{ mg}/\text{m}^2$ IV and cytarabine 100

CONFIDENTIAL

mg/m² IV) on Days 1 and 3. Quizartinib (30 mg by PO once daily) will resume on Day 6 and continue through Day 21. If re-induction is required, a minimum 72-hour period is necessary between the dose of quizartinib on Day 21 and the administration of CPX-351 with re-induction.

If it is believed by the PI and/or sub-investigator that a patient with prolonged Grade ≥ 3 toxicity after the induction phase would be likely to experience additional toxicities during the consolidation phase, the patient could bypass the consolidation phase and proceed to a cellular intervention or the maintenance phase. Any patient with neutropenia or thrombocytopenia lasting ≥ 56 days from the initiation of CPX-351 will not receive consolidation and will instead proceed to the maintenance phase.

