9.10 Time to Absolute Neutrophil Count (ANC) and Platelet Count Recovery

Time to neutrophil recovery is defined as the time from each CPX-351 cycle Day 1 to when the peripheral ANC is $\geq 500/\mu\text{L}$. Time to platelet recovery is defined as the time from each CPX-351 cycle to when the peripheral blood platelet count is $> 50,000/\mu\text{L}$. Delayed neutrophil recovery is defined as having an ANC $< 500/\mu\text{L}$ > 56 days from each CPX-351 cycle Day 1. Delayed platelet recovery is defined as having a platelet count $< 50,000$ > 56 days from each CPX-351 cycle Day 1.

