10. STATISTICAL CONSIDERATIONS

10.1 Statistical Design

This is a multi-center, open-label, two-part prospective Phase II study of patients with relapsed or refractory FLT3-ITD mutation-positive AML. The study is designed to assess the safety and tolerability as well as the efficacy of administering CPX-351 with quizartinib, a second-generation FLT3 inhibitor.

A response rate (CR + CRi) of $\geq 50\%$ is targeted with 40% or less considered unacceptable. This is assumed to be an acceptable estimate based on CR + CRi/CRp of 48.2% reported with quizartinib monotherapy in a relapsed or refractory patient with FLT3-ITD AML (Cortes et al 2019). Of note, prior FLT3-targeting inhibitor exposure is permitted on this study. However, patients receiving a prior FLT3-targeting inhibitor were excluded in the QUANTUM-R study. Expected CR+CRi in relapsed or refractory patients receiving standard intensive or non-intensive salvage chemotherapy harboring an FLT3 mutation is 27% (Cortes et al 2019). The estimated response in those with relapsed/refractory FLT3-ITD AML receiving CPX-351 alone cannot be estimated. However, in a poor-risk EPI patient population, CR+CRi was reported as 39.3% (Cortes et al 2015). However, FLT3-ITD mutation presence was not utilized in the generation of EPI prognostication, and those with an FLT3-ITD mutation could in fact have a reduced response within all EPI risk groups. Thus, the expected response must be based upon the QUANTUM-R study of those receiving standard salvage options harboring an FLT3-ITD mutation.

In the safety lead-in, 10 patients will be enrolled to receive CPX-351 with quizartinib. If > 3 patients experience delayed neutrophil count recovery > 56 days or delayed thrombocytopenia recovery > 56 days from the first day on the study regimen, or if > 3 patients develop a non-hematologic toxicity, defined as a Grade 4 non-hematologic AE determined to be probably related to the combined treatment or a Grade 4 neutropenia, then the study will be terminated.

Assuming safety parameters are met, the first 10 patients will be followed for response in Part 2 of the study.

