10.5 Analysis Time Points

10.5.1 Safety Review

The safety lead-in consists of the first 10 patients enrolled. If >3 patients experience delayed neutrophil count recovery >56 days from the first day receiving the study regimen, defined as having a peripheral blood ANC <500/ μ L without evidence of residual disease by BM biopsy, or if >3 patients develop a non-hematologic toxicity, defined as a Grade 4 non-hematologic AE determined to be probably related to the combined treatment, then the study will be terminated.

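### Section 10.5.1 omits delayed platelet recovery from the lead-in stopping rule that the Synopsis, Section 5 and Section 10.1 all state, and narrows the neutrophil limb

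*Combined protocol and SAP*

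**What the plan says.** The lead-in gate is stated in four places, and all four count from the first day on the regimen.

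- Section 5 stops the study if more than 3 patients have delayed neutrophil recovery beyond 56 days or "delayed thrombocytopenia recovery >56 days from the first day on the study regimen".
- The Synopsis (Statistical Methodology) has the same platelet limb: "or delayed thrombocytopenia recovery >56 days from the first day on the study regimen".
- Section 10.1 has it in shortened form: "days or delayed thrombocytopenia recovery".
- Section 10.5.1 lists delayed neutrophil recovery, defined as ANC <500/µL, and passes straight to the non-haematologic limb: "without evidence of residual disease by BM biopsy, or if >3 patients develop a non-hematologic toxicity". Platelets do not appear.

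None of the four gives a platelet threshold. One exists in Section 9.10 ("Delayed platelet recovery is defined as having a platelet count" below 50,000 beyond 56 days), and Section 2.3.2 uses the same level and the same 56 days. The gate cites neither section.

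**The concern.** Section 10.5.1 is where someone running the lead-in review would look for the rule, and it is the only version without platelets. Section 1.5 calls pancytopenia, with potentially prolonged neutropenia and thrombocytopenia, the most anticipated side effect of the combination. A review run strictly from 10.5.1 could let enrolment of the further 24 patients go ahead when the other three statements require termination. The residual-disease qualifier acts in the same direction: a patient with prolonged neutropenia and persistent leukaemia counts under the other three texts but not under 10.5.1. Nothing in the documents says which statement governs.

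**Working it through.** The plan states no operating characteristic for the gate, so there is no figure of its own to reproduce. The check is a comparison of the texts followed by an illustration.

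**Comparison of the haematologic limbs**

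| Place | Neutrophils | Platelets | ANC <500/µL stated | No residual disease required |
|---|---|---|---|---|
| Synopsis | yes | yes | no | no |
| Section 5 | yes | yes | no | no |
| Section 10.1 | yes | yes | no | no |
| Section 10.5.1 | yes | no | yes | yes |

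**A case that separates them.** Suppose 4 of 10 patients still have platelets below 50,000/µL after Day 56 and all 10 have recovered neutrophils. Under Section 5 the count is 4, which exceeds 3, and the study ends. Under 10.5.1 the count is 0 and this limb does not stop it.

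**Inputs for the illustration**

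- n = 10, stop if more than 3 (Sections 5 and 10.5.1).
- CPX-351 induction rates beyond Day 42, without quizartinib (Section 7.5.2): 17% for ANC <500 and 28% for platelets <50.
- Assumed: Day-56 rates are 50% or 100% of the Day-42 rates, giving 0.085 or 0.17 for neutrophils and 0.14 or 0.28 for platelets.
- Assumed: every neutrophil-delayed patient is also platelet-delayed. The combined rate then equals the platelet rate, the smallest it can be.
- Set aside: the residual-disease qualifier in 10.5.1, and the Grade 4 neutropenia clause that the other three texts carry and 10.5.1 does not.

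**Formula.** P(X > 3) = 1 − Σ C(10,k) p^k (1−p)^(10−k), for k = 0 to 3.

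- p = 0.17: 1 − (0.1552 + 0.3178 + 0.2929 + 0.1600) = 0.074
- p = 0.28: 1 − (0.0374 + 0.1456 + 0.2548 + 0.2642) = 0.298

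| Assumed Day-56 rates | Neutrophils only | With platelet limb |
|---|---|---|
| 50% of Day-42 | 0.007 | 0.040 |
| 100% of Day-42 | 0.074 | 0.298 |

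**Sensitivity to counting.** With full overlap it makes no difference whether neutrophil and platelet patients are pooled or counted in separate limbs. With no overlap it does. Pooled counting uses p = 0.085 + 0.14 = 0.225 and p = 0.17 + 0.28 = 0.45, giving 0.169 and 0.734. Separate limbs give 0.047 and 0.365. The text does not say which is meant.

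**The case against.** The strongest reply is that the texts can be read together. Three of the four say the study will be terminated for delayed platelets, one of them within the statistical section. Section 10.5.1 sits under Analysis Time Points, and it neither claims to override the others nor says that the study continues when platelets are delayed. That is a fair reading and probably the intended one. It bears on how serious the point is, but a stopping rule should not depend on the reader reconciling four statements. Excluding neutropenia with residual disease is also a defensible way to separate toxicity from leukaemia, and Section 5.2 already calls for a marrow at Day 42 when ANC is below 500/µL. The difficulty is that the exclusion appears in only one of the four texts.

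Three stronger readings are tempting, and the documents do not support them.

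- *That the plan has no platelet threshold.* It does, in Sections 9.10 and 2.3.2. Only the cross-reference is missing.
- *That 0.298 − 0.074 = 0.224 is the probability that Sections 5 and 10.5.1 disagree.* It is not. It sets aside two wording differences, assumes full overlap, and treats a Day-42 rate as a Day-56 rate.
- *That the clock is wrong for re-induced patients.* Section 5.2.2 allows re-induction ("If there is a PR at the recovery BM biopsy, patients may be re-treated"), and Section 9.10 counts "56 days from each CPX-351 cycle Day 1". The gate counts from the first day on the regimen, and the consolidation bar runs "days from the initiation of CPX-351 will not receive consolidation and will instead proceed to the maintenance phase". A patient re-induced on Day 28-42 would reach study Day 56 on re-induction Day 29-15 (56 − 28 + 1; 56 − 42 + 1). But the gate and the bar consistently run from first treatment, and a conservative stopping clock can coexist with a per-cycle endpoint. The effect on the gate is also small: with an assumed 20-40% re-induced and the 28% platelet rate (p = 0.056-0.112), P(>3 of 10) is 0.002-0.019. Restarting the clock would postpone the decision for such a patient by 27-41 days (28 + 55 − 56; 42 + 55 − 56), which loosens a safety rule. How these patients count is for the sponsor to clarify; it is not an error.

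**Conclusion.** The inconsistency is real and rests on the current text alone: 10.5.1 lacks the platelet limb that the other three statements carry and defines the neutrophil limb more narrowly. It should be corrected because the decision at stake is study termination, and the omitted event is the commoner one in the only background rates the plan gives.

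The size cannot be fixed from the documents. The ranges of 0.007-0.074 and 0.040-0.298 are illustrations for the haematologic limbs only. They depend on the assumed Day-56 rates, on full overlap, on setting aside the qualifier and the Grade 4 neutropenia clause, and on rates for CPX-351 without quizartinib. If Day-56 rates were only 25% of the Day-42 rates, both probabilities would be small (0.001 and 0.004). The inconsistency in the text does not depend on any of these figures.

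**What to change.** Use one gate sentence, word for word, in the Synopsis, Section 5, Section 10.1 and Section 10.5.1. It should:

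- include delayed platelet recovery alongside delayed neutrophil recovery;
- cite the Section 9.10 thresholds (ANC <500/µL, platelets <50,000/µL);
- say whether neutrophil and platelet patients are pooled, each counted once, or counted separately against the limit of 3;
- say whether the residual-disease qualifier applies and, if so, to which limb;
- keep the existing clock from first treatment.

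Making the four texts identical also obliges the sponsor to decide whether the Grade 4 neutropenia clause stays. A line on how re-induced patients are counted would be a useful clarification.

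The cost is a text amendment. Platelets come from the same blood count as the ANC, so the added limb needs no test beyond those the neutrophil limb already needs. The downside is a higher chance of stopping than under 10.5.1 alone: in the illustration, up by 0.033 (0.040 − 0.007) to 0.224 (0.298 − 0.074). Adding the platelet limb to 10.5.1 does not itself raise the chance of stopping relative to what the other three sections already require.

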Objectives:	
Primary Objectives The primary objectives of this study are to:
 
 • Determine the safety and tolerability of CPX-351 (cytarabine:daunorubicin liposome complex) with quizartinib in patients with relapsed or refractory fms-like tyrosine kinase 3 (FLT3)-internal tandem duplication (ITD) mutation-positive acute myeloid leukemia (AML). • Determine the overall complete morphologic (per World Health Organization) and molecular remission rate of CPX-351 and quizartinib in patients with relapsed or refractory FLT3-ITD mutation-positive AML. 
Secondary Objectives The secondary objectives of this study are to:
 
 • Define the time to absolute neutrophil count and platelet count recovery • Define the number of patients proceeding to an allogeneic stem cell transplant (alloHCT) • Determine time to disease progression or duration of response • Determine event-free survival • Determine overall survival • Define the percentage of patients who develop late responses • Define the number of patients who can receive consolidation and maintenance therapy on this study • Define the treatment-related mortality rate of this combination • Determine the percentage of patients who achieve a PR or molecular complete remission (CR) • Determine the mean elapsed time for patients to achieve molecular CR • Determine whether quizartinib is tolerable after alloHCT or donor lymphocyte infusion. 	
Study Design:	This is a multi-center, non-randomized, open-label, two-part prospective Phase II clinical trial in patients with relapsed or refractory FLT3-ITD mutation-positive AML. The study is designed to assess the safety and tolerability as well as the efficacy of administering CPX-351 (cytarabine:daunorubicin liposome complex) with quizartinib, a second-generation FLT3 inhibitor. The plan for administration is divided into three phases: induction, consolidation, and maintenance. Approximately 34 patients are planned to be screened and enrolled.	

CONFIDENTIAL

STUDY DRUG: QUIZARTINIB
PROTOCOL DATE: 10 AUGUST 2020

DEVELOPMENT INNOVATIONS STUDY NUMBER: AML 48
VERSION 4.0

	
A total of 10 patients will be enrolled in the safety lead-in, which is designated as Part 1 of the study. If ≥ 8 patients meet the pre-specified safety parameters, an additional 24 patients will be enrolled in Part 2 of the study. All patients will be assessed for response.

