1.5 Risks and Benefits

The risks associated with the study derive from the novel combination of CPX-351 with quizartinib. The most anticipated side effect is pancytopenia, with potentially prolonged neutropenia and thrombocytopenia compared to standard induction or salvage chemotherapy. In a randomized study in AML patients, CPX-351 demonstrated a median time to absolute neutrophil count (ANC) \geq 1000 of 36 days compared to 32 days with standard cytarabine and daunorubicin (7+3). In addition, there was a statistically significant increase in Grade 3 or Grade 4 infections. However, infection-related mortality has not been demonstrated. In the same study, platelet count recovery to $>$ 100,000 was 37 days compared to 28 days in those receiving 7+3. Quizartinib in combination with cytarabine and daunorubicin was associated with 21% of study participants showing Grade \geq 3 toxicity for both neutropenia and thrombocytopenia. However, there was no prolonged period of pancytopenia, suggesting that the proposed novel combination of CPX-351 and quizartinib may not contribute to a longer period of myelosuppression than what is expected with CPX-351 alone. Grade 3 and higher febrile neutropenia was identified in 63.5% of patients receiving CPX-351 alone (Lancet et al 2014) and in 47% of patients receiving quizartinib alone (Altman et al 2018).

CPX-351 contains daunorubicin, an anthracycline that has a known association with cardiomyopathy at threshold doses of 550 mg/m². Patients will be excluded if their cumulative dose of an anthracycline exceeds this threshold. To date, quizartinib has not been associated with cardiomyopathy or a reduction in the ejection fraction. Quizartinib has been associated with QT prolongation in a dose dependent manner. In study AC220-007 (Quantum-R) in the relapse/refractory FLT3+ AML population, Eight (3.3%) subjects in the quizartinib arm had ECG QTcF values $>$ 500 ms (Grade 3 QTcF) by central ECG reading. (Quizartinib Investigator Brochure 2020. CPX-351 has not been associated with significant QTc prolongation (CPX-351 US package insert [USPI]). For this study, these cardiac risk factors will need to be monitored

CONFIDENTIAL

STUDY DRUG: QUIZARTINIB
PROTOCOL DATE: 10 AUGUST 2020

DEVELOPMENT INNOVATIONS STUDY NUMBER: AML 48
VERSION 4.0

and accounted for independently. Dose modifications for QTcF prolongation will be based upon pre-specified monitoring and criteria (see Section 8).

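### The safety lead-in gate is stated five times in three conflicting versions, none declared governing, so the same 10 patients can give different decisions

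*Combined protocol and SAP*

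**What the plan says.** Five places in the current text state the gate. The amendment summary is not counted here.

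- **Synopsis, Study Design.** A condition for going on: "If ≥ 8 patients meet the pre-specified safety parameters, an additional 24 patients will be enrolled in Part 2 of the study". The parameters are not listed there, and nothing is said about what follows if only 7 patients meet them.
- **Synopsis, Statistical Methodology; Section 5; Section 10.1.** A termination rule at more than 3 patients. The hematologic limb covers delayed neutrophil recovery and also, in Section 5, "or delayed thrombocytopenia recovery >56 days from the first day on the study regimen". The toxicity limb in Section 5 ends "probably related to the combined treatment, or a Grade 4 neutropenia, then the study will be terminated". The Statistical Methodology entry has the same content. Section 10.1 drops a comma: "probably related to the combined treatment or a Grade 4 neutropenia, then the study will be terminated".
- **Section 10.5.1, Safety Review.** A termination rule at more than 3 patients. Neutrophil delay counts only if ANC is below 500/µL "without evidence of residual disease by BM biopsy, or if >3 patients develop a non-hematologic toxicity". The toxicity limb is "defined as a Grade 4 non-hematologic AE determined to be probably related to the combined treatment, then the study will be terminated". Platelets and Grade 4 neutropenia are not mentioned.

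Section 9.10 separately defines delayed neutrophil recovery (ANC below 500/µL) and delayed platelet recovery (below 50,000), both beyond 56 days, with no residual-disease qualifier. No section says which statement of the gate takes precedence.

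**The concern.** Safety and tolerability are a primary objective, and this is the only numerical safety gate found in the documents before Part 2 enrolls. The termination rule is mandatory in its wording, yet its content depends on the section opened. If the choice between versions is made after the lead-in data are known, a regimen that one section would stop could expand, or a tolerable one could be stopped.

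Two of the differences concern the toxicity the plan most expects. Section 1.5 says: "The most anticipated side effect is pancytopenia, with potentially prolonged neutropenia and thrombocytopenia compared to standard induction or salvage chemotherapy". Section 7.5.2 reports, for CPX-351 induction, thrombocytopenia prolonged beyond Day 42 in 28% and neutropenia in 17%. So 10.5.1 leaves out the cytopenia that is more often prolonged, while Section 5 read literally counts neutropenia that recovers on time.

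**Working it through.** The plan gives no operating characteristics for the gate, so there is no figure to reproduce. The check is a comparison of texts, followed by one illustrative calculation.

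**Content of the three versions**

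| Element | A: Synopsis, Study Design | B: Synopsis, Statistical Methodology; Section 5; Section 10.1 | C: Section 10.5.1 |
|---|---|---|---|
| Cut-off | go if ≥8 of 10 pass | terminate if >3 | terminate if >3 |
| Platelet delay >56 days | not listed | counted | absent |
| Neutrophil delay >56 days | not listed | counted, no disease qualifier | counted only without residual disease |
| Grade 4 neutropenia, any duration | not listed | present (clear in two places, ambiguous in 10.1) | absent |
| Related Grade 4 non-hematologic AE | not listed | counted | counted |

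**The same 10 patients under each version**

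1. *Exactly 3 with a related Grade 4 non-hematologic AE, nothing else.* Version A: 10 − 3 = 7 pass, fewer than 8, so Part 2 does not open (taking this event to be one of the unlisted parameters). Version C: 3 is not more than 3, so the study continues. Version B also continues if its neutropenia phrase is set aside.
2. *Exactly 4 with platelet delay beyond 56 days, nothing else.* Version B terminates. Version C continues.
3. *Exactly 4 with Grade 4 neutropenia that recovers on time, nothing else.* Version B, read literally in Section 5 and the Statistical Methodology entry, terminates. Version C continues.
4. *Exactly 4 with neutrophil delay and residual leukemia.* Version B counts all 4 and terminates. Version C counts none.

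None of these four cases depends on an assumed event rate.

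**Illustration of the cut-off difference.** Suppose all texts used one patient-level definition of failure with true rate p. The ≥8-pass condition and the >3 rule then disagree only when exactly 3 of 10 fail:

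P(X = 3) = C(10,3) · p³ · (1 − p)⁷

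- p = 0.10: 120 × 0.001 × 0.4783 = 0.057
- p = 0.20: 120 × 0.008 × 0.2097 = 0.201
- p = 0.30: 120 × 0.027 × 0.08235 = 0.267
- p = 0.40: 120 × 0.064 × 0.02799 = 0.215

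At p = 0.20, the chance of not opening Part 2 (3 or more fail) is 32.2%, against a 12.1% chance of terminating (4 or more fail). At p = 0.30 the pair is 61.7% and 35.0%. The rates p are assumptions.

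**The case against.** **Section 10.5.1 is the operative section and the rest is summary.** That would be a natural convention, but the documents do not state it. The synopsis also disagrees with itself (at least 8 must pass, against more than 3 failing). And Section 9.10 defines platelet delay, and defines neutrophil delay without a disease qualifier, which fits Section 5 better than 10.5.1.

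**The Grade 4 neutropenia phrase is a drafting slip.** It may well be: it sits inside a definition of non-hematologic toxicity, and in Section 10.1 it can be read as something the adverse event is related to. A reader might infer that the trial is nearly certain to be terminated on this phrase. The documents do not support that, because they give no Grade 4 neutropenia rate. Section 1.5 says "Grade 3 and higher febrile neutropenia was identified in 63.5% of patients receiving CPX-351 alone", which is a different event. Over assumed rates from 21% to 90%, the chance that more than 3 of 10 are affected runs from 14% to above 99.9%, so the result only mirrors the input. What stands is that the phrase appears in three places attached to mandatory termination.

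**Failures should simply be counted per patient across all limbs.** A reader might infer that the conflict requires this. It does not. The four >3 statements count by limb, so a cross-limb count would be a new and stricter rule. Take independent events at assumed rates of 8.5% neutrophil delay, 14% platelet delay (half the Day 42 figures) and 10% Grade 4 AE. Under the Section 5 text without the neutropenia phrase, with the two delays pooled, termination would rise from about 16% to 33%. Under 10.5.1 it would rise from about 2% to 8%. That is a design decision, not a correction.

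**Conclusion.** The plan is wrong as written: one mandatory gate has three incompatible versions, and following the text can give opposite decisions on the same patients. This rests on the wording alone.

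The size is less certain. The 20% to 27% figure is the chance of landing on the contested count of exactly 3, at assumed failure rates of 20% to 30%. It holds only if all texts share one patient-level definition. It should not be read as the overall probability that the versions disagree, because they also differ in what they count and in how they count it. The documents give no Day 56 rates and no rates for the combination, so no overall probability can be calculated from them.

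Nor does the synopsis go condition say that the study terminates at 3 failures. It says only when Part 2 opens, and leaves the alternative unstated.

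**What to change.** State one rule in Section 10.5.1, and have both synopsis entries, Section 5 and Section 10.1 refer to it. In that rule:

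- Keep the >3 cut-off already used in four of the five places, and reword the synopsis go condition so that Part 2 opens unless a 10.5.1 criterion is met.
- Define delay by Section 9.10: ANC below 500/µL or platelets below 50,000/µL beyond Day 56.
- Include the platelet limb in 10.5.1.
- State whether the residual-disease qualifier applies.
- Delete the Grade 4 neutropenia phrase, since delayed neutrophil recovery is already a limb.
- State whether neutrophil and platelet delays are pooled toward >3, and whether counting is by limb or by patient. If the sponsor prefers one count per patient across all limbs, treat it as a design change and report its operating characteristics.

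The cost is protocol wording. No patients or procedures are added, and the efficacy sample size in Section 10.2 is unaffected.
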